9.2.9 WBC A₃AR Expression

At selected sites, a blood sample will be obtained at the Cycle 1 Day 1 (Baseline) visit, prior to dosing. 2.5 mL of blood are to be collected. The complete procedure is detailed in the laboratory manual provided by the central laboratory.

Sampling will be repeated at the beginning of every odd-numbered cycle, unless waived by the Sponsor.

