12.4.2 Efficacy Data

All efficacy analyses will be performed for the ITT Population. Tumor response will be analyzed for the PP Population, with the analyses for the ITT Population being primary.

Time to event variables will be summarized using the number observed, number censored, median, and 25th and 75th percentiles from Kaplan-Meier curves. Data will be summarized using descriptive statistics (number of subjects (n), mean, median, standard deviation, minimum, and maximum) for continuous variables. Categorical variables will be summarized using frequencies and percentages.

Between-treatment comparisons with respect to OS, TTP, and PFS will be performed using logrank tests, with Cox's proportional hazards regression model used for supportive analyses to assess the impact of covariates. Tumor lesion measurements and changes from baseline will be summarized by cycle and treatment. Objective response rates and DC rates will be presented and between-treatment comparisons will be performed using the normal approximation to the binomial distribution by treatment for each even-numbered cycle. Between-treatment comparisons with respect to AFP will be performed using Analysis of Covariance (ANCOVA) with the value at baseline value used as a covariate and frequencies of subjects with AFP levels <20, 20-200, or >200 ng/mL will be presented by treatment for each cycle.

Liver Chemistry Tests, INR, and viral load will be summarized using descriptive statistics and clinically significant abnormalities will be listed. Additionally, between-treatment comparisons with respect to these laboratory parameters will be performed using ANCOVA with the baseline value used as a covariate.

The relationship between WBC A₃AR expression and clinical response will be assessed by providing the counts and percentages for Overall Response by Change from Baseline (CFB) in A₃AR expression categorized as less than or at least the median by treatment at each visit.

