#### 7.6.5 BIOMARKERS

The biomarker α-fetoprotein (AFP) will be assessed at Baseline, at Day 1 of each cycle, and at the follow-up visit. Summary statistics for AFP levels and CFB in AFP levels will be provided for the ITT Population by treatment and visit. Between-treatment comparisons will be performed by visit using Analysis of Covariance (ANCOVA) with CFB as the dependent variable and Baseline as the covariate. Summary statistics for AFP and CFB in AFP will be provided for each level of Overall Response for the ITT Population by treatment. Distribution of Overall Response will be presented for subjects with AFP levels <20, 20-200, or >200 ng/mL and for subjects with AFP levels above or at most the pooled median by treatment and cycle; the percentages will be calculated using number of subjects within each category defined by AFP levels as the denominator for each treatment.

WBC A3AR expression will be assessed at Baseline and at Day 1 of each odd-numbered cycle. Summary statistics for WBC A3AR expression and CFB in WBC A3AR expression will be provided for the ITT Population by treatment and visit. Summary statistics for CFB in WBC A3AR expression will be provided for each level of Overall Response for the ITT Population by treatment. To assess the relationship between Overall Response and changes in WBC A3AR at each visit, the distribution of Overall Response will be presented for subjects with WBC A3AR less than the pooled median and for subjects with WBC A3AR at least the pooled median at each post-baseline visit.

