CFB=Change from Baseline
Baseline=Cycle 1 Day 1
Missing data for intermediate visits are imputed using LOCF.

Source: Listing 16.2.6.4

Programming Note: Continue for all visits (Day 1 for each odd-numbered cycle through Cycle 11), including CFB.

Table 14.2.3.2 WBC A3AR expression at Baseline by Overall Response ITT Population

			CF102	Placebo
Visit	Overall Response	Statistic	(N=xx)	(N=xx)
Cycle 3 Day 1	CR	n	xx	XX
		Mean (SD)	xxx.x (xxx.xx)	xxx.x (xxx.xx)
		Median	XXX.X	XXX.X
		Min, Max	XXX, XXX	XXX, XXX
	PR	n	xx	XX
		Mean (SD)	xxx.x (xxx.xx)	xxx.x (xxx.xx)
		Median	xxx.x	XXX.X
		Min, Max	xxx, xxx	XXX, XXX
	SD	n	XX	XX
		Mean (SD)	xxx.x (xxx.xx)	xxx.x (xxx.xx)
		Median	xxx.x	XXX.X
		Min, Max	XXX, XXX	XXX, XXX
	PD	n	XX	XX
		Mean (SD)	xxx.x (xxx.xx)	xxx.x (xxx.xx)
		Median	xxx.x	XXX.X
		Min, Max	XXX, XXX	XXX, XXX
CFB at Cycle 3 Day 1	CR	n	XX	xx
,		Mean (SD)	xxx.x (xxx.xx)	xxx.x (xxx.xx)
		Median	xxx.x	XXX.X
		Min, Max	XXX, XXX	XXX, XXX
	PR	n	XX	XX
		Mean (SD)	xxx.x (xxx.xx)	xxx.x (xxx.xx)
		Median	xxx.x	xxx.x
		Min, Max	XXX, XXX	XXX, XXX
	SD	n	xx	XX
		Mean (SD)	xxx.x (xxx.xx)	xxx.x (xxx.xx)
		Median	xxx.x	xxx.x
		Min, Max	XXX, XXX	XXX, XXX
	PD	n	хх	хх
		Mean (SD)	xxx.x (xxx.xx)	xxx.x (xxx.xx)
		Median	xxx.x	xxx.x
		Min, Max	XXX, XXX	XXX, XXX

Baseline=Cycle 1 Day 1
Missing data for intermediate visits are imputed using LOCF.

Source: Listings 16.2.6.3.1, 16.2.6.4

Programming Note: Continue for all visits (Day 1 for each odd-numbered cycle through Cycle 11), including CFB.

Table 14.2.3.3 Overall Response by CFB for WBC A3AR expression ITT Population

	CFB for WBC A3AR		CF102	Placebo
Visit	expression	Overall Response (n, %)	(N=xx)	(N=xx)
Cycle 3 Day 1	< xxx.x (M)	CR	xx (xx.x)	xx (xx.x)
		PR	xx (xx.x)	xx (xx.x)
		SD	xx (xx.x)	xx (xx.x)
		PD	xx (xx.x)	xx (xx.x)
		Total	XX	XX
	>= xxx.x (M)	CR	xx (xx.x)	xx (xx.x)
		PR	xx (xx.x)	xx (xx.x)
		SD	xx (xx.x)	xx (xx.x)
		PD	xx (xx.x)	xx (xx.x)
		Total	XX	XX
Cycle 5 Day 1	< xxx.x (M)	CR	xx (xx.x)	xx (xx.x)
		PR	xx (xx.x)	xx (xx.x)
		SD	xx (xx.x)	xx (xx.x)
		PD	xx (xx.x)	xx (xx.x)
		Total	XX	XX
	>= xxx.x (M)	CR	xx (xx.x)	xx (xx.x)
		PR	xx (xx.x)	xx (xx.x)
		SD	xx (xx.x)	xx (xx.x)
		PD	xx (xx.x)	xx (xx.x)
		Total	XX	XX

CFB=Change from Baseline

Baseline=Cycle 1 Day 1

Percentages are calculated using the number of subjects in the ITT Population for each treatment as the denominator. M=pooled median of CFB for WBC A3AR expression at the specified visit

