Visit	AFP (ng/mL)	Overall Response (n, %)	(N=xx)	(N=xx)
Cycle 3 Day 1	<20	CR	xx (xx.x)	xx (xx.x)
		PR	xx (xx.x)	xx (xx.x)
		SD	xx (xx.x)	xx (xx.x)
		PD	xx (xx.x)	xx (xx.x)
		Total	XX	XX
	20-200	CR	xx (xx.x)	xx (xx.x)
		PR	xx (xx.x)	xx (xx.x)
		SD	xx (xx.x)	xx (xx.x)
		PD	xx (xx.x)	xx (xx.x)
		Total	XX	XX
	>200	CR	xx (xx.x)	xx (xx.x)
		PR	xx (xx.x)	xx (xx.x)
		SD	xx (xx.x)	xx (xx.x)
		PD	xx (xx.x)	xx (xx.x)
		Total	XX	XX
Cycle 5 Day 1	<20	CR	xx (xx.x)	xx (xx.x)
		PR	xx (xx.x)	xx (xx.x)
		SD	xx (xx.x)	xx (xx.x)
		PD	xx (xx.x)	xx (xx.x)
		Total	XX	XX
	20-200	CR	xx (xx.x)	xx (xx.x)
		PR	xx (xx.x)	xx (xx.x)
		SD	xx (xx.x)	xx (xx.x)
		PD	xx (xx.x)	xx (xx.x)
		Total	XX	XX
	>200	CR	xx (xx.x)	xx (xx.x)
		PR	xx (xx.x)	xx (xx.x)
		SD	xx (xx.x)	xx (xx.x)
		PD	xx (xx.x)	xx (xx.x)
		Total	xx	xx

Percentages are calculated using the number of subjects in the ITT Population in each category defined by AFP for each treatment as the denominator.

Missing data for intermediate visits are imputed using LOCF.

Source: Listings 16.2.6.3.1, 16.2.6.4

Programming Notes: Continue for all visits (Day 1 for each odd-numbered cycle). AFP is collected with lab data.

Table 14.2.4.4

Overall Response by CFB for Alpha-fetoproterin (AFP)

ITT Population

•			CF102	Placebo
Visit	CFB for AFP	Overall Response (n, %)	(N=xx)	(N=xx)
Cycle 3 Day 1	<xxx.x (m)<="" td="">CR	xx (xx.x)	xx (xx.x)	</xxx.x>	CR	xx (xx.x)	xx (xx.x)
		PR	xx (xx.x)	xx (xx.x)
		SD	xx (xx.x)	xx (xx.x)
		PD	xx (xx.x)	xx (xx.x)
		Total	XX	XX
	>= xxx.x (M)	CR	xx (xx.x)	xx (xx.x)
		PR	xx (xx.x)	xx (xx.x)
		SD	xx (xx.x)	xx (xx.x)
		PD	xx (xx.x)	xx (xx.x)
		Total	XX	XX
Cycle 5 Day 1	< xxx.x (M)	CR	xx (xx.x)	xx (xx.x)
		PR	xx (xx.x)	xx (xx.x)
		SD	xx (xx.x)	xx (xx.x)
		PD	xx (xx.x)	xx (xx.x)
		Total	XX	XX
	>= xxx.x (M)	CR	xx (xx.x)	xx (xx.x)
		PR	xx (xx.x)	xx (xx.x)
		SD	xx (xx.x)	xx (xx.x)
		PD	xx (xx.x)	xx (xx.x)
		Total	XX	XX

CFB=Change from Baseline

Baseline=Cycle 1 Day 1

M=pooled median of CFB for AFP at the specified visit

Percentages are calculated using the number of subjects in the ITT Population in each category defined by

AFP for each treatment as the denominator.

Missing data for intermediate visits are imputed using LOCF.

Source: Listings 16.2.6.3.1, 16.2.6.4

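### Shell Table 14.2.3.3 divides each A3AR category's response counts by the whole ITT arm, so its printed percentages are not response rates within the category

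*SAP*

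**What the plan says.** **The table.** Shell Table 14.2.3.3 crosses Overall Response (CR, PR, SD, PD and a Total row) with two categories of change from baseline in A3AR, by arm and visit. The cut-point is defined in a footnote: "M=pooled median of CFB for WBC A3AR expression at the specified visit". The denominator is defined in another: "Percentages are calculated using the number of subjects in the ITT Population for each treatment as the denominator".

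**The data behind it.** Protocol 9.2.9 limits the measurement: "At selected sites, a blood sample will be obtained". Sampling is repeated at odd-numbered cycles and the sponsor may waive it. SAP Section 8 and the shell footnote carry values forward for missed intermediate visits. Neither creates values for subjects who were never sampled, and Section 8 imputes nothing after discontinuation.

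**The parallel biomarker.** AFP has no site restriction. Shells 14.2.4.3 and 14.2.4.4 divide by the number of subjects "in the ITT Population in each category defined by AFP for each treatment as the denominator". SAP 7.6.5 gives the same rule for AFP and gives no denominator for A3AR.

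**The split variable.** Protocol 12.4.2 splits change from baseline, "categorized as less than or at least the median by treatment at each visit". The shell also splits change from baseline. SAP 7.6.5 opens with "To assess the relationship between Overall Response and changes in WBC" A3AR, but its operative words are that "the distribution of Overall Response will be presented for subjects with WBC A 3 AR less than the pooled median", which is the value and not the change.

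**The concern.** A table of response by biomarker category is read by comparing the two categories: of the subjects whose A3AR fell, what share had stable disease, and of those whose A3AR rose, what share? That needs each category's own size as denominator. With the arm's full ITT count, a percentage mixes two things: how often the response occurred within the category, and how many subjects happened to be in the category at that visit. The second depends on which sites sampled, on waivers, on dropout and on where the pooled median falls, and none of these is tumor response.

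Exploring the relation between A3AR and clinical response is a listed secondary objective, and this is the only planned display of response by A3AR category. The biomarker with partial collection is also the one given the arm-wide denominator, while AFP has the category denominator. The documents give no reason for the difference.

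**Working it through.** The plan states no figure for this table, so there is none to reproduce. The check is on the footnote's rule.

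**Inputs**
- Arm sizes: about 78 subjects at 2:1 (protocol 12.2), so 78 × 2/3 = 52 on CF102 and 78 × 1/3 = 26 on placebo.
- Share f of an arm with a usable A3AR change at a visit: not in the documents. This is an assumption, shown from 25% to 100%.
- Even split of the arm at the median: an assumption, relaxed below.

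**Formula.** Let x be the count with a given response in a category, m the category size and N the arm's ITT count.

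Printed percentage = x/N = (x/m) × (m/N).

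The within-category rate is x/m, so the footnote scales it by m/N. With an even split, m = f × N/2 and the scale factor is f/2, whatever the arm size.

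| Share with A3AR data, f (assumed) | Scale factor f/2 | A within-category rate of 40% prints as |
|---|---|---|
| 25% | 0.125 | 5% |
| 50% | 0.25 | 10% |
| 75% | 0.375 | 15% |
| 100% | 0.50 | 20% |

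The four response percentages in a category then add up to f/2 instead of 100%. Even with every subject sampled, the printed figure is half the rate. With the category as denominator, the printed figure is 40% in every row.

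**Numerical example (hypothetical counts).** CF102 arm of 52, half sampled (26), 13 in each category, 6 of the low category with SD. Within category: 6/13 = 46.2%. Printed: 6/52 = 11.5%.

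**Uneven split (hypothetical counts).** A pooled median halves the two arms together, not each arm. Take 26 sampled CF102 subjects falling 16 low and 10 high, with SD in 6 and 5.
- Within category: 6/16 = 37.5% low against 5/10 = 50.0% high.
- As printed: 6/52 = 11.5% low against 5/52 = 9.6% high.

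The ordering reverses.

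**Split variable, side by side.** Protocol 12.4.2: change from baseline. Shell title, column header and footnote: change from baseline. SAP 7.6.5: lead-in refers to changes, operative clause splits the value. SAP Section 9 does not list this as a departure from the protocol. The AFP median-split sentence in SAP 7.6.5 has the same mismatch: it speaks of AFP levels, while shell 14.2.4.4 splits change from baseline.

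**The case against.** The strongest reply is that nothing is lost. Every cell prints the count beside the percentage, and every category has a Total row by arm and visit. In the example above a reader sees 6 with a Total of 13 and can work out 46.2%. Table 14.2.3.1 gives the number with A3AR values by arm and visit, Table 14.2.3.2 summarizes A3AR by response, and the listings carry subject-level data. No p-value hangs on these percentages, and the plan treats A3AR as an exploratory efficacy variable. All of this stands, and it limits the point to the printed percentages.

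Three stronger readings are tempting, and the documents do not support them.

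- *The A3AR objective cannot be read from this table.* It can, from the counts and Totals.
- *Unsampled subjects are counted as non-responders.* They enter none of the four response rows. PD shrinks by the same factor as SD, so the relative distribution within a category is unchanged. What fails is the comparison between categories of different size.
- *Unequal sampling produces a false difference between arms.* Printed percentages would be distorted differently if the share with data differed by arm. But sampling is chosen by site and treatment is randomized and blinded, so no systematic imbalance in who is sampled is shown. Differential dropout could cause one, but the documents give no figure for it among A3AR subjects.

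The mismatch over the split variable is a slip in the SAP text and does not make the table wrong: the shell already follows the protocol.

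**Conclusion.** The footnote is wrong as written for a response-by-category table. Followed literally, it prints joint percentages of the arm in place of response rates within A3AR category. The shrinkage is m/N: about one half with full sampling and an even split, and about one quarter if half the arm has data. The low-versus-high comparison can reverse when the pooled median divides an arm unevenly.

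The sampled share and the even split are assumptions, because the documents give no number of A3AR sites or subjects. The reversal rests on hypothetical counts and shows what is possible, not what occurred.

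Severity is minor: the rates can be rebuilt from what is printed, the analysis is descriptive and exploratory, and overall survival is unaffected.

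**What to change.** 1. **Table 14.2.3.3 footnote.** Change the denominator to the number of ITT subjects in each category defined by change from baseline in A3AR, for each treatment, as Tables 14.2.4.3 and 14.2.4.4 do for AFP. State that this is the category's Total row, with carried-forward values counted as the table already specifies, so that the four percentages add up to 100%.
2. **SAP 7.6.5, A3AR sentence.** Say that the pooled-median split is on change from baseline in WBC A3AR, as in protocol 12.4.2 and the shell.
3. **SAP 7.6.5, AFP median-split sentence.** Reconcile it with Table 14.2.4.4 in the same way.

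No new sample-size row is needed, since Table 14.2.3.1 and the Total rows already show the numbers with data. The cost is one footnote, one line of program and two sentences of SAP text, with a note of the change in SAP Section 9.

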# Listing of Discontinuations Due to Adverse Events Safety Population

Site/		Date of	Date of Withdrawal from Trial		
Subject	Treatment	Final Dose	or Dosing	Primary Reason	Specify
xxx/xxxx	XXXXXXXX	DD/MM/YY	DD/MM/YY	xxxxxxxxxxxxxxxx	XXX

Includes only subjects with AE recorded as reason for withdrawal from dosing or trial Source: Listings 16.2.1, 16.2.7

Table 14.3.6.1

Clinical Laboratory Evaluations: Hematology
Safety Population

Parameter (Units)	Visit	Statistic	CF102 (N=xx)	Placebo (N=xx)
XXXXXXXXX	Pre-Study	n	XX	(N-XX)
	Fie-Study			
(UNITS)		Mean(SD) Median	xxx.xx (xxx.xxx)	XXX.XX (XXX.XXX)
			XXX.XX	XXX.XXX
	Cycle 4 Day 4	Min, Max	XXX.X, XXX.X	XXX.X, XXX.X
	Cycle 1 Day 1	n M (OD)	XXX	XXX
		Mean(SD)	xxx.xx (xxx.xxx)	xxx.xx (xxx.xxx)
		Median	XXX.XX	XXX.XXX
		Min, Max	XXX.X, XXX.X	XXX.X, XXX.X
	Cycle 1 Day 8	n	XXX	XXX
		Mean(SD)	xxx.xx (xxx.xxx)	xxx.xx (xxx.xxx)
		Median	XXX.XX	XXX.XXX
		Min, Max	XXX.X, XXX.X	XXX.X, XXX.X
	CFB to Cycle 1 Day 8	n	XXX	XXX
		Mean(SD)	xxx.xx (xxx.xxx)	xxx.xx (xxx.xxx)
		Median	xxx.xx	XXX.XXX
		Min, Max	XXX.X, XXX.X	XXX.X, XXX.X
	XXXXX	n	xxx	xxx
		Mean(SD)	xxx.xx (xxx.xxx)	xxx.xx (xxx.xxx)
		Median	xxx.xx	xxx.xxx
		Min, Max	XXX.X, XXX.X	XXX.X, XXX.X
	CFB to xxxxx	n	XXX	XXX
		Mean(SD)	xxx.xx (xxx.xxx)	xxx.xx (xxx.xxx)
		Median	XXX.XX	XXX.XXX
		Min, Max	XXX.X, XXX.X	XXX.X, XXX.X

CFB=Change From Baseline

Baseline=Cycle 1 Day 1 (or Pre-Study if <= 3 days prior to Cycle 1 Day 1 or if value at Cycle 1 Day 1 is missing)

Includes visits with at least 4 subjects in either treatment group

Source: Listing 16.2.8.1

Programming Notes: Continue for all parameters and all visits (Days 1, 8, and 15 for Cycle 1, and Days 1 and 15 for subsequent cycles), including CFB. Include visits with at least 4 subjects in either treatment group. The following tables will use the above format:

Table 14.3.6.2 Clinical Laboratory Evaluations: Blood Chemistry (Safety Population) with Source: Listing 16.2.8.2 and

Table 14.3.6.3 Clinical Laboratory Evaluations: Coagulation (Safety Population) with Source: Listing 16.2.8.3.

Table 14.3.6.4 Clinical Laboratory Evaluations: Thyroid Function Safety Population

Darameter (Unite)	\/ioit	Ctatiatia	CF102	Placebo
Parameter (Units)	Visit	Statistic	(N=xx)	(N=xx)
Γ3 (Unit)	Pre-Study	n	XX	XX
		Mean(SD)	xxx.xx (xxx.xxx)	xxx.xx (xxx.xxx)
		Median	XXX.XX	XXX.XXX
		Min, Max	XXX.X, XXX.X	XXX.X, XXX.X
	Cycle 1	n	XXX	XXX
		Mean(SD)	xxx.xx (xxx.xxx)	XXX.XX (XXX.XXX)
		Median	XXX.XX	XXX.XXX
		Min, Max	XXX.X, XXX.X	XXX.X, XXX.X
	Cycle 2	n	XXX	XXX
		Mean(SD)	xxx.xx (xxx.xxx)	xxx.xx (xxx.xxx)
		Median	XXX.XX	XXX.XXX
		Min, Max	XXX.X, XXX.X	XXX.X, XXX.X
	CFB to Cycle 2	n	xxx	XXX
	•	Mean(SD)	xxx.xx (xxx.xxx)	xxx.xx (xxx.xxx)
		Median	XXX.XX	XXX.XXX
		Min, Max	XXX.X, XXX.X	XXX.X, XXX.X
	XXXXX	n	XXX	xxx
		Mean(SD)	xxx.xx (xxx.xxx)	xxx.xx (xxx.xxx)
		Median	XXX.XX	XXX.XXX
		Min, Max	XXX.X, XXX.X	XXX.X, XXX.X
	CFB to xxxxx	n ´	xxx	XXX
		Mean(SD)	xxx.xx (xxx.xxx)	xxx.xx (xxx.xxx)
		Median	XXX.XX	XXX.XXX
		Min, Max	XXX.X, XXX.X	XXX.X, XXX.X

CFB=Change From Baseline

Baseline=Cycle 1 (or Pre-Study if <= 3 days prior to Cycle 1 Day 1 or if value at Cycle 1 Day 1 is missing) Includes visits with at least 4 subjects in either treatment group

Source: Listing 16.2.8.5

Programming Note: Continue for T4 (Unit) and TSH (Unit) and all cycles with at least 4 subjects in either treatment group.

Table 14.3.7.1

ECOG Performance Status
Safety Population

		CF102	Placebo	
Visit	ECOG PS, n (%)	(N=xx)	(N=xx)	
Pre-Study	0	xx (xx.x)	xx (xx.x)	
-	1	xx (xx.x)	xx (xx.x)	
	2	xx (xx.x)	xx (xx.x)	
	3	xx (xx.x)	xx (xx.x)	
	4	xx (xx.x)	xx (xx.x)	
	Total	xx	XX	
Cycle 1 Day 1	0	xx (xx.x)	xx (xx.x)	
	1	xx (xx.x)	xx (xx.x)	
	2	xx (xx.x)	xx (xx.x)	
	3	xx (xx.x)	xx (xx.x)	
	4	xx (xx.x)	xx (xx.x)	
	Total	xx	XX	
Cycle 2 Day 1	0	xx (xx.x)	xx (xx.x)	
	1	xx (xx.x)	xx (xx.x)	
	2	xx (xx.x)	xx (xx.x)	
	3	xx (xx.x)	xx (xx.x)	
	4	xx (xx.x)	xx (xx.x)	
	Total	xx	xx	
Cycle 3 Day 1	0	xx (xx.x)	xx (xx.x)	
	1	xx (xx.x)	xx (xx.x)	
	2	xx (xx.x)	xx (xx.x)	
	2 3	xx (xx.x)	xx (xx.x)	
	4	xx (xx.x)	xx (xx.x)	
	Total	xx	xx	

0=Normal activity, 1=Symptoms but ambulatory, 2= In bed <50% of time, 3=In bed >50% of time, 4=100% bedridden Baseline=Cycle 1 Day 1 (or Pre-Study if <= 3 days prior to Cycle 1 Day 1 or if value at Cycle 1 Day 1 is missing) Percentages are calculated using the number of subjects in the Safety Population for each treatment as the denominator. Includes visits with at least 4 subjects in either treatment group Source: Listing 16.2.9.3

Programming Notes: Continue for all cycles with at least 4 subjects in either treatment group. Include '4' only for cycles with a non-zero frequency for at least one treatment.

Table 14.3.7.2 Change from Baseline in ECOG Performance Status Safety Population

	CFB in	CF102	Placebo
Visit	ECOG PS, n (%)	(N=xx)	(N=xx)
Cycle 2 Day 1	Decrease	xx (xx.x)	xx (xx.x)
	No Change	xx (xx.x)	xx (xx.x)
	Increase	xx (xx.x)	xx (xx.x)
	Total	XX	XX
Cycle 3 Day 1	Decrease	xx (xx.x)	xx (xx.x)
•	No Change	xx (xx.x)	xx (xx.x)
	Increase	xx (xx.x)	xx (xx.x)
	Total	XX	XX

CFB=Change from Baseline

Baseline=Cycle 1 Day 1 (or Pre-Study if <= 3 days prior to Cycle 1 Day 1 or if value at Cycle 1 Day 1 is missing)

Percentages are calculated using the number of subjects in the Safety Population for each treatment as the denominator. Includes visits with at least 4 subjects in either treatment group

Source: Listing 16.2.9.3

Programming Note: Continue for all visits (Day 1 for all cycles) with at least 4 subjects in either treatment group.

Table 14.3.8

Vital Signs And Weight Safety Population

Parameter (Units)	Visit	Statistic	CF102 (N=xx)	Placebo (N=xx)
			,	, ,
Systolic BP (mmHg)	Pre-Study	n (OD)	XX	XX
		Mean(SD)	xxx.xx (xxx.xxx)	xxx.xx (xxx.xxx)
		Median	XXX.XX	XXX.XXX
		Min, Max	XXX.X, XXX.X	XXX.X, XXX.X
	Baseline	n	XX	XX
		Mean(SD)	xxx.xx (xxx.xxx)	xxx.xx (xxx.xxx)
		Median	xxx.xx	xxx.xxx
		Min, Max	XXX.X, XXX.X	XXX.X, XXX.X
	Cycle 1 Day 1			
	Hour 1	n	xx	XX
		Mean (SD)	xxx.x (xxx.xx)	xxx.x (xxx.xx)
		Median	xxx.x	xxx.x
		Min, Max	xxx, xxx	XXX, XXX
	CFB to	,	7001, 7001	7001, 7001
	Cycle 1 Day 1 Hour 1	n	XX	XX
	Cycle : Bay i riour i	Mean (SD)	xxx.x (xxx.xx)	xxx.x (xxx.xx)
		Median	XXX.X	XXX.X
		Min, Max	XXX, XXX	XXX, XXX

BP=Blood Pressure

BMI=Body mass index

CFB= Change From Baseline

Baseline=Cycle 1 Day 1 (or Pre-Study if <= 3 days prior to Cycle 1 Day 1 or if value at Cycle 1 Day 1 is missing)

Includes visits with at least 4 subjects in either treatment group

Source: Listings 16.2.9.1, 16,2.9.2

Programming Notes: Continue for Diastolic BP (mmHg), Pulse (beats/min), Temperature (deg C), Respiratory Rate (/min), Weight (kg), and BMI (kg/m2) and visits (Days 1 and 15 of each cycle, Day 8 of Cycle 1, and Hours 1, 2, 3, 4, 6 and 8 on Cycle 1 Day 1) with CFB. Weight (kg) is not recorded at Hours 1, 2, 3, 4, 6 and 8 on Cycle 1 Day 1. Include visits with at least 4 subjects in either treatment group.

Table 14.3.9.1 Electrocardiogram (ECG) Parameters Safety Population

_			CF102	Placebo
Parameter	Visit	Statistic	(N=xx)	(N=xx)
Heart Rate (bpm)	Pre-Study	n	XXX	XXX
(25)		Mean (SD)	xxx.x (xxx.xx)	xxx.x (xxx.xx)
		Median	XXX.X	XXX.X
		Min, Max	XXX, XXX	XXX, XXX
	Baseline	n	XXX	XXX
		Mean (SD)	xxx.x (xxx.xx)	xxx.x (xxx.xx)
		Median	XXX.X	XXX.X
		Min, Max	XXX, XXX	XXX, XXX
	Cycle 1 Day 1 Hour 2	n	XXX	XXX
		Mean (SD)	xxx.x (xxx.xx)	xxx.x (xxx.xx)
		Median	XXX.X	XXX.X
		Min, Max	XXX, XXX	XXX, XXX
	CFB to Cycle 1 Day 1 Hour 2	n	XXX	XXX
		Mean (SD)	xxx.x (xxx.xx)	xxx.x (xxx.xx)
		Median	XXX.X	XXX.X
		Min, Max	XXX, XXX	XXX, XXX
QTcF (msec) (1)	Pre-Study	n	xxx	XXX
	·	Mean (SD)	xxx.x (xxx.xx)	xxx.x (xxx.xx)
		Median	xxx.x	XXX.X
		Min, Max	XXX, XXX	XXX, XXX
	Baseline	n	xxx	XXX
		Mean (SD)	xxx.x (xxx.xx)	xxx.x (xxx.xx)
		Median	XXX.X	xxx.x
		Min, Max	XXX, XXX	XXX, XXX
	Cycle 1 Day 1 Hour 2	n	xxx	XXX
	•	Mean (SD)	xxx.x (xxx.xx)	xxx.x (xxx.xx)
		Median	xxx.x	xxx.x
		Min, Max	XXX, XXX	XXX, XXX
	CFB to Cycle 1 Day 1 Hour 2	n	XXX	xxx
	, ,	Mean (SD)	xxx.x (xxx.xx)	xxx.x (xxx.xx)
		Median	xxx.x	xxx.x
		Min, Max	XXX, XXX	XXX, XXX

 QTcF= QT Correction- Fridericia

Programming Notes: Continue for QRS Complex (msec), PR Interval (msec), and QTcF (msec) in that order and all visits (pre-Study, pre-dose at all visits, and at 2, 4, and 6 hours post-dose on Days 1 and 8 of Cycle 1) with CFB. Compute QTcF=QT\*(HR/60)1/3. Include visits with at least 4 subjects in either treatment group.

CFB= Change From Baseline

Baseline=Cycle 1 Day 1 Hour 0 (or Pre-Study if value at Cycle 1 Day 1 is missing) Includes visits with at least 4 subjects in either treatment group Source: Listing 16.2.10.1

Table 14.3.9.2

Categorical Electrocardiogram (ECG) Parameters
Safety Population

			CF102	Placebo
Parameter	Visit	Response, n (%)	(N=xx)	(N=xx)
Overall Impression	Pre-Study	Normal	XXX (XX.X)	xxx (xx.x)
•	·	NCS	xxx (xx.x)	xxx (xx.x)
		CS	xxx (xx.x)	xxx (xx.x)
		Total	XX	XX
	Baseline	Normal	XXX (XX.X)	xxx (xx.x)
		NCS	xxx (xx.x)	xxx (xx.x)
		CS	xxx (xx.x)	xxx (xx.x)
		Total	XX	XX
	Cycle 1 Day 1 Hour 2	Normal	xxx (xx.x)	xxx (xx.x)
	· •	NCS	xxx (xx.x)	xxx (xx.x)
		CS	xxx (xx.x)	xxx (xx.x)
		Total	XX	XX
	Cycle 1 Day 1 Hour 4	Normal	xxx (xx.x)	xxx (xx.x)
		NCS	xxx (xx.x)	xxx (xx.x)
		CS	xxx (xx.x)	xxx (xx.x)
		Total	XX	XX
	Cycle 1 Day 1 Hour 6	Normal	XXX (XX.X)	xxx (xx.x)
		NCS	xxx (xx.x)	xxx (xx.x)
		CS	xxx (xx.x)	xxx (xx.x)
		Total	XX	XX
	Cycle 1 Day 8 Pre-Dose	Normal	xxx (xx.x)	xxx (xx.x)
		NCS	xxx (xx.x)	xxx (xx.x)
		CS	xxx (xx.x)	xxx (xx.x)
		Total	XX	XX
	Cycle 1 Day 8 Hour 2	Normal	xxx (xx.x)	xxx (xx.x)
	-	NCS	xxx (xx.x)	xxx (xx.x)
		CS	xxx (xx.x)	xxx (xx.x)
		Total	xx	XX

NCS= Abnormal-not clinically significant (NCS)

CS= Abnormal-clinically significant (CS)

Baseline=Cycle 1 Day 1 Hour 0 (or Pre-Study if value at Cycle 1 Day 1 is missing)

Percentages are calculated using the number of subjects in the Safety Population for each treatment as the denominator.

Includes visits with at least 4 subjects in either treatment group

Source: Listing 16.2.10.2.

Programming Notes: Continue for ST Segment and Cardiac Rhythm (Normal, Abnormal, and Total) and all visits (Pre-Study visit, Days 1 and 15 of all cycles, Day 8 of Cycle 1, and at 2, 4, and 6 hours post-dose on Day 1 of Cycle 1, and at Follow-up). Include visits with at least 4 subjects in either treatment group.

Table 14.3.10.1 Physical Examination at Pre-Study Visit Safety Population

		CF102	Placebo
Body System	Response, n (%)	(N=xx)	(N=xx)
General Appearance	Normal	xxx (xx.x)	XXX (XX.X)
	Abnormal	xxx (xx.x)	xxx (xx.x)
	Total	xxx	XXX
Head and Neck	Normal	xxx (xx.x)	xxx (xx.x)
	Abnormal	xxx (xx.x)	xxx (xx.x)
	Total	xxx	XXX
Eyes, Ears, Nose, Throat	Normal	xxx (xx.x)	xxx (xx.x)
	Abnormal	xxx (xx.x)	xxx (xx.x)
	Total	XXX	XXX
Skin	Normal	xxx (xx.x)	xxx (xx.x)
	Abnormal	xxx (xx.x)	xxx (xx.x)
	Total	xxx	XXX
Chest / Lungs / Breast	Normal	xxx (xx.x)	xxx (xx.x)
	Abnormal	xxx (xx.x)	xxx (xx.x)
	Total	xxx	XXX
Heart	Normal	xxx (xx.x)	xxx (xx.x)
	Abnormal	xxx (xx.x)	xxx (xx.x)
	Total	XXX	xxx
Neurological	Normal	xxx (xx.x)	xxx (xx.x)
	Abnormal	xxx (xx.x)	xxx (xx.x)
	Total	XXX	XXX
Other (1)	Normal	xxx (xx.x)	xxx (xx.x)
(-,	Abnormal	xxx (xx.x)	xxx (xx.x)
	Total	XXX	XXX

(1) Subjects with more than one assessment of "Other" are counted once. Percentages are calculated using the number of subjects in the Safety Population for each treatment as the denominator.

Abnormalities are provided in the listing.

Source: Listing 16.2.11 .1

Programming Notes: Include other body systems. Subjects with more than one assessment of "Other" are counted once. Do not include "Not Assessed".

Table 14.3.10.2 Physical Examination Safety Population

Visit	Clin. Sig.	CF102	Placebo
	Changes (1), n (%)	(N=xx)	(N=xx)
Cycle 1 Day 1	Yes	XXX (XX.X)	XXX (XX.X)
	No	xxx (xx.x)	xxx (xx.x)
	Total	XXX	XXX
Cycle 1 Day 8	Yes	xxx (xx.x)	xxx (xx.x)
	No	xxx (xx.x)	xxx (xx.x)
	Total	XXX	XXX
Cycle 1 Day 15	Yes	xxx (xx.x)	xxx (xx.x)
	No	xxx (xx.x)	xxx (xx.x)
	Total	XXX	XXX
Cycle 2 Day 1	Yes	xxx (xx.x)	XXX (XX.X)
	No	xxx (xx.x)	xxx (xx.x)
	Total	XXX	XXX
Cycle 2 Day 15	Yes	xxx (xx.x)	xxx (xx.x)
	No	xxx (xx.x)	xxx (xx.x)
	Total	xxx	XXX

 Are there any clinically significant changes from the physical examination conducted at the previous assessment?

Source: Listing 16.2.11.2

Programming Note: Continue for all visits (Days 1, 8, and 15 of Cycle 1 and Days 1 and 15 of subsequent cycles) with at least 4 subjects in either treatment group.

Percentages are calculated using the number of subjects in the Safety Population for each treatment as the denominator.

Abnormalities associated with clinically significant changes are provided in the listing. Includes visits with at least 4 subjects in either treatment group

Table 14.3.11 **Prior and Concomitant Medications** Safety Population

	CF102	Placebo
ATC Level 3 Class, n (%)	(N=xx)	(N=xx)
None	xx (xx.x)	xx (xx.x)
Class 1	xx (xx.x)	xx (xx.x)
Class 2	xx (xx.x)	xx (xx.x)

Includes medications taken within 30 days prior to Screening Visit.

Percentages are calculated using the number of subjects in the Safety Population for each treatment as the denominator.

Sum of percentages may exceed 100% because subjects could take Concomitant Medications within more than one ATC Level 3 Class.

Source: Listing 16.2.12

Programming Note: Continue for all observed Therapeutic Classes Individual medications are not tabulated; only the ATC Level 3 Class. Check that no subject has "None" for Complications with another response.

